4.9 Descriptive outcomes analysis

4.9.1 Positive Surgical Margins

The PSM will be reported descriptively, reporting the number and percentage of participants in each of the PSM category, by arm.

4.9.2 Time to erectile function recovery

Descriptive analysis of time to erectile function recovery (IIEF-5 scores larger or equal to 15) will be performed displaying the Kaplan Meier survival curve by arm.

IIEF5 data included for this analysis will be those from visit 2 to visit 4, as described in section 3.3. Follow-up time will start on day of surgery and until visit 4. Patients will be assumed as not recovered at entry. Patients will be censored when first reaching $IIEF-5 \geq 15$ or at date of last available IIEF-5.

Kaplan Meier curves will be shown until 15 months.

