3.6.2 Time to erectile function recovery

This will be defined as the time from surgery to the time of first reaching an IIEF-5 score larger or equal to 15.

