3.6.4 Time to urinary continence recovery

This will be defined as the time from surgery to the time of first reaching a ICIQ score of 5 or below.

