4.9.3 Time to urinary continence

Descriptive analysis of time to urinary continence (ICIQ scores less or equal to 5) will be performed displaying the Kaplan Meier survival curve by arm.

ICIQ data included for this analysis will be those from visit 2 to visit 4, as described in section 3.3. Follow-up time will start on day of surgery and until visit 4. Patients will be assumed as incontinent at entry. Patients will be censored when first reaching $ICIQ \leq 5$ or at date of last available ICIQ.

Kaplan Meier curves will be shown until 15 months.

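### SAP 4.9.2 and 4.9.3 call recovery a censoring, although SAP 3.6.2 and 3.6.4 make it the event: a minor wording error in two descriptive Kaplan-Meier analyses

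*SAP*

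**What the plan says.** SAP 3.6.2 defines time to erectile function recovery as "the time from surgery to the time of first reaching an IIEF-5 score larger or equal to 15". SAP 3.6.4 defines the continence outcome in the same way, as "time from surgery to the time of first reaching a ICIQ score of 5 or below".

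SAP 4.9.2 gives the analysis for the first of these, which "will be performed displaying the Kaplan Meier survival curve by arm". Follow-up runs from the day of surgery to visit 4. On the starting state it says "Patients will be assumed as not recovered at entry". The exit rule is one sentence: "Patients will be censored when first reaching" an IIEF-5 of at least 15, "or at date of last available IIEF-5".

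SAP 4.9.3 repeats the rule for an ICIQ of 5 or less, with the alternative exit "or at date of last available ICIQ". Both curves are to be drawn to 15 months.

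SAP 1.1 and 3.2 list both outcomes as descriptive.

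**The concern.** A Kaplan-Meier analysis needs one piece of information about each patient's exit time: whether the exit was the event or a censoring. In both sections a single verb, 'censored', covers the only two exits. Patients start as not recovered (or incontinent), so recovery is the only change of state that could be an event, and that change is labelled as censoring. Section 3.6 and section 4.9 cannot both be followed as written.

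What is at stake is limited but real. SAP 2.1 gives pre-specification as the document's purpose, and SAP 2.3 says most analysis programs will be written before unblinding. Someone checking a correct program against 4.9.2 or 4.9.3 would find that it departs from the written rule. A program that followed the rule exactly would produce an empty analysis.

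**Working it through.** The SAP states no event count or expected recovery for these two curves, so there is no figure of its own to reproduce. The check has two parts.

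**1. The exit rules set against the definitions**

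| | Erectile function | Continence |
|---|---|---|
| Outcome definition | Time to first IIEF-5 ≥15 (3.6.2) | Time to first ICIQ ≤5 (3.6.4) |
| State at entry | Not recovered (4.9.2) | Incontinent (4.9.3) |
| Exit 1 as written | IIEF-5 ≥15: censored | ICIQ ≤5: censored |
| Exit 2 as written | Last available IIEF-5: censored | Last available ICIQ: censored |
| Exit coded as event | None | None |

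The Kaplan-Meier estimate is S(t) = ∏(1 − d_j/n_j) over event times up to t, where d_j is the number of events and n_j the number at risk. If every exit is a censoring, every d_j is 0. Then S(t) = 1 and estimated recovery, 1 − S(t), is 0% in both arms up to 15 months. This follows from the rule alone and needs no assumed rate.

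**2. Illustration of the two codings**

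Assumptions, for contrast only:
- 182 patients per arm, which is half of the 364 evaluable in SAP 1.4.
- Everyone is followed to 12 months.
- Cumulative recovery at 3, 6 and 12 months is 10%, 18% and 28% (control) and 15%, 27% and 42% (NeuroSAFE). The 12-month values borrow the 28% and 42% of SAP 1.4, which refer to IIEF-5 ≥21 and not ≥15. The 3- and 6-month values are invented.

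In whole patients, cumulative recoveries are 18, 33 and 51 in the control arm and 27, 49 and 76 in the NeuroSAFE arm.

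With recovery as the event:
- Control: S(12) = (164/182) × (149/164) × (131/149) = 131/182 = 0.720, so recovery is 28.0% with 51 events.
- NeuroSAFE: S(12) = (155/182) × (133/155) × (106/133) = 106/182 = 0.582, so recovery is 41.8% with 76 events.

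With recovery as censoring, as written, the same data give 0 events and 0% in both arms.

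**The case against.** The best defence is that the SAP, read as a whole, leaves no doubt about the event. Sections 3.6.2 and 3.6.4 define it. Sections 4.9.2 and 4.9.3 each open by naming time to recovery with its threshold, and they state that patients begin in the unrecovered state. In that setting 'censored' can sensibly mean only that follow-up ends. There is no rival workable analysis to choose between, so the slip gives no room for selective analysis and has no direction of bias. A curve with no events would be noticed on the first run, and SAP 2.1 allows limited, justified adjustments.

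Nothing tested depends on the curves either. The primary and secondary analyses (SAP 4.7 and 4.8) are linear regressions on scores. The subgroup analyses specified in 4.10 and the missing-data sensitivity analyses in 4.11 do not use the curves. Recovery by arm is also to be reported as a binary outcome at 3, 6 and 12 months (SAP 3.2, 3.6.1 and 3.6.3).

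All of this stands, and it sets the severity. It does not make the sentence right: the reader still has to override a stated rule to reach the intended analysis.

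A reader might infer more, namely that the two time-to-recovery outcomes cannot be reported or that flat curves will be published. The documents do not support that. It would require the analysts to disregard both the outcome definitions and the opening lines of the same sections.

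**Conclusion.** The wording is wrong in both sections and contradicts the SAP's own outcome definitions. Taken literally, it gives 0 events per arm and 0% estimated recovery throughout. That figure describes the literal rule and is not a forecast of what will be reported. The judgement that this is a drafting slip rests on 3.6.2, 3.6.4 and the opening lines of 4.9.2 and 4.9.3, which agree on the event.

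Severity is minor: two descriptive curves are affected, and no primary, secondary or subgroup test is. Confidence is high on the wording. The 51 and 76 events above depend on assumed rates, and the conclusion does not rest on them.

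**What to change.** Replace the censoring sentence in each section.

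- **SAP 4.9.2:** The event occurs at the date of the first IIEF-5 score of 15 or more. Patients who do not reach it are censored at the date of their last available IIEF-5.
- **SAP 4.9.3:** The event occurs at the date of the first ICIQ score of 5 or less. Patients who do not reach it are censored at the date of their last available ICIQ.

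The cost is a short rewording in each of two sections. It needs no new data and changes no endpoint or threshold. Programs that already code recovery as the event need no change.

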4.9.3 Time to urinary continence

Descriptive analysis of time to urinary continence (ICIQ scores less or equal to 5) will be performed displaying the Kaplan Meier survival curve by arm.

ICIQ data included for this analysis will be those from visit 2 to visit 4, as described in section 3.3. Follow-up time will start on day of surgery and until visit 4. Patients will be assumed as incontinent at entry. Patients will be censored when first reaching $ICIQ \leq 5$ or at date of last available ICIQ.

Kaplan Meier curves will be shown until 15 months.

4.9.4 Oncological outcome

We will report descriptively the oncological outcome during the first year, presenting the frequency and percentage in each category, by arm.

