	
Comparison of the proportion of men with BCR between NeuroSAFE and control arms within 12 months of surgery. BCR will be considered to have occurred when the post operative PSA measures <math>>0.2\text{ng/mL}</math>, or where the PSA level is less than <math>0.2\text{ ng/mL}</math> but the trajectory suggests inevitable rise above <math>0.2\text{ ng/mL}</math> according to the clinician looking after the patient. If PSA fails to nadir after surgery, this will not be considered BCR as this is probably related to micro metastatic disease not detected by preoperative imaging.
 
For further descriptive analyses, sub-group analyses, and sensitivity analyses please see body of protocol, Outcomes Section.
 
3) Additional oncological treatments
 
 
‘Adjuvant treatment’ refers to men who undergo additional cancer treatment without having BCR. A descriptive analysis of the proportion of men undergoing adjuvant oncological treatments (ADT and/or radiotherapy and/or chemotherapy) at or before 12 months of surgery will be conducted.
 
‘Salvage treatment’ refers to men who undergo additional cancer treatment following BCR. A descriptive analysis of the proportion of men undergoing adjuvant oncological treatments (ADT and/or radiotherapy and/or chemotherapy) at or before 12 months of surgery will be conducted.
 
 
4) Quality of Life
 
 
A comparison of the proportion of men achieving the best quality of life according to the EQ-5D-5L between intervention and control arms.
 
Analysis of EQ-5D-5L scores to produce QALYs at 12 months by arm
 
Analysis of RAND36 scores to produce QALYs at 12 months by arm
 
Analysis of EPIC-26 scores at 36, 48 and 60 months after surgery and a maximum frequency of annually thereafter
 
 
5) Positive Surgical Margins (PSM)

--	--

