## 5 HYPOTHESES & OBJECTIVES

### 5.1 Hypotheses

- Men undergoing NeuroSAFE RARP will experience superior EF recovery compared to men undergoing standard RARP.
- Men undergoing NeuroSAFE RARP will experience improved recovery of urinary continence at 3 months following surgery compared to men undergoing standard RARP.
- Men undergoing NeuroSAFE RARP will experience the same rates of cure from surgery compared to those undergoing standard RARP.

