### 6.2 Secondary

1. To evaluate the differences in urinary continence recovery in the early period following treatment (3 and 6 months) between men undergoing standard RARP (control arm) and NeuroSAFE RARP (intervention arm).
2. To evaluate the differences in oncological outcomes (including BCR and administration of adjuvant/salvage treatments) between men undergoing standard RARP vs. NeuroSAFE RARP at 12 months. Additional analysis is intended at 5 years post-surgery.
3. To evaluate differences in overall quality of life outcomes between men undergoing standard RARP vs NeuroSAFE RARP at 12, 24, 36, 48 and 60 months after surgery and a maximum frequency of annually thereafter.
4. To evaluate differences in recovery of erections after 12-months and up to 2 years between men undergoing standard RARP vs NeuroSAFE RARP
5. Economic analysis to assess health resource use between standard RARP vs NeuroSAFE RARP at 12 months and up to 2 years post treatment.

---

 Evaluation after 12 months dependent on future funding

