#### 7.2.2.2. BCR

Comparison of the proportion of men with BCR between NeuroSAFE and control arms within 12 months of surgery. BCR will be considered to have occurred when the post operative PSA measures  $>0.2$  ng/mL, or where the PSA level is less than 0.2 ng/mL but the trajectory suggests inevitable rise above 0.2 ng/mL according to the clinician looking after the patient. If PSA fails to nadir after surgery, this will not be considered BCR as this is probably related to micro metastatic disease not detected by preoperative imaging. Patients with demonstration of metastases on imaging will not be considered as BCR for the same reason.

- Follow up time of 12 months is defined as cumulative time up to the 12-month visit. Patients visits after more than 13.5 months post-surgery will not be included (12 months + 6 weeks max visit window).
- Additional descriptive analysis will report recurrences across all patients at the following times: Within 3 months (+/- visit window) and within 6 months (+/- visit window).
- Descriptive analysis of BCR for each arm according to
  - (a) Gleason grade
  - (b) TNM stage
  - (c) pre-operative PSA level
  - (d) routinely used risk classifiers (D'Amico, CAPRA, EAU) (e) time of recurrence.

If patients have a low but detectable PSA level the frequency of testing would be increased from the usual schedule (3,6,9,12 months) depending on the trajectory and level of concern of the clinician looking after the patient.

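### The protocol's between-arm comparison of 12-month biochemical recurrence becomes percentages by arm in the SAP, with no planned difference or confidence interval, and the BCR definitions need reconciling

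*SAP*

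**What the plan says.** Protocol 5.1 lists three hypotheses. The third is: "Men undergoing NeuroSAFE RARP will experience the same rates of cure from surgery compared to those undergoing standard RARP". The matching objective in Protocol 6.2 begins "To evaluate the differences in oncological outcomes (including BCR and administration of adjuvant/salvage treatments" and applies at 12 months. Protocol 7.2.2.2 then sets the endpoint: "Comparison of the proportion of men with BCR between NeuroSAFE and control arms within 12 months of surgery". In that section only the secondary breakdowns (by 3 and 6 months, grade, stage, PSA and risk group) are called descriptive.

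Protocol 12.2.4 gives methods for the primary outcome and for the first secondary outcome (continence). It names no test or interval for BCR.

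The SAP classes oncological outcome as descriptive (1.1 and 3.2), rewords the objective so that outcomes are reported rather than differences evaluated (1.2.2), and plans this analysis in 4.9.4: "We will report descriptively the oncological outcome during the first year, presenting the frequency and percentage in each category, by arm".

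On the definition, Protocol 7.2.2.2 counts a PSA above 0.2 ng/mL as BCR, and also a PSA below that level where "the trajectory suggests inevitable rise above 0.2 ng/mL according to the clinician looking after the patient". It adds "Patients with demonstration of metastases on imaging will not be considered as BCR for the same reason", and on timing "Patients visits after more than 13.5 months post-surgery will not be included (12 months + 6 weeks max visit window". SAP 3.6.5 instead requires a PSA below 0.2 at visit 2 followed by a PSA of 0.2 or more at visit 3 or 4.

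**The concern.** The case for NeuroSAFE is that more nerves can be spared without loss of cancer control. Erectile function and continence each get an adjusted difference with a confidence interval (SAP 4.7 and 4.8). Cancer control gets two columns of percentages. If those percentages look alike, a reader may take them as support for equal cure, and nothing in the plan obliges the report to say how large an excess of BCR the data leave open.

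The definition matters for the same reason. While the passages disagree, the same man can be a BCR event under one and not under another, and his later treatment can carry different labels. Some of the routes rest on clinical judgement, and the surgeon is not blinded (Protocol 9.2). It is safer to settle the rules before allocation is revealed.

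**Working it through.** **1. Is a difference or interval planned anywhere else?** Four other provisions come close, and none supplies one for BCR in the whole trial population.

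- Protocol 12.2.4 says p-values for secondary outcomes will not be adjusted, but gives no BCR method.
- SAP 4.1.3 fixes the level of any interval reported at 95%, without assigning one to BCR.
- SAP 4.10.3 allows differences in descriptive outcomes, optionally and only in men without a bilateral nerve-sparing recommendation.
- Protocol 13.1.1 lets the iDMC advise stopping for a BCR excess at p<0.01. That is monitoring, not the final analysis.

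**2. Definitions side by side.**

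| Point | Protocol | SAP |
|---|---|---|
| Trajectory below 0.2 | Counts as BCR (2, 7.2.2.2) | No such route (3.6.5): a treated man goes to early salvage treatment, an untreated man to no recurrence |
| Label for treatment after trajectory-based BCR | Salvage under section 2, which says it "refers to men who undergo additional cancer treatment following BCR"; adjuvant under 7.2.2.3, because the PSA threshold was not reached | Category named early salvage but defined by receipt of adjuvant treatment (3.6.5) |
| Time limit | Visits after 13.5 months excluded (7.2.2.2) | No PSA window, as a declared choice (3.3) |
| Metastases on imaging | Not BCR (7.2.2.2); section 2 is silent | Not mentioned (3.6.5) |
| Recurrence by 3 months | To be described (7.2.2.2) | Impossible: PSA of 0.2 or more at visit 2 is persistence (3.6.5), and visit 2 is the first scheduled post-operative PSA (3.1; Protocol 7.4) |
| Threshold | Above 0.2 (7.2.2.2) | 0.2 or above (3.6.5) |

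It is also unclear which PSA values count. Protocol 7.2.2.2 mentions a month-9 test and extra tests for men with detectable PSA. Both assessment schedules list PSA at visits only. SAP 3.3 says all available PSA data are used, while SAP 3.6.5 defines the categories by visit.

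**3. The sample size.** SAP 1.4 assumes 42% v 28%, 80% power and two-sided 5%. With mean proportion 0.35,

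n per arm = [1.96·√(2·0.35·0.65) + 0.842·√(0.28·0.72 + 0.42·0.58)]² / 0.14² ≈ 181.02, rounded up to 182, so 364 in total.

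This reproduces the SAP's evaluable number. These are erectile-function rates; the documents give no BCR rate, margin or power. The number of men with PSA data is therefore assumed to lie between 182 per arm (364/2) and 202 per arm (404/2).

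**4. Precision for BCR.** Newcombe's method takes Wilson limits (l, u) for each proportion p and gives, for d = p₁ − p₂,

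lower = d − √[(p₁−l₁)² + (u₂−p₂)²]; upper = d + √[(u₁−p₁)² + (p₂−l₂)²].

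Example with 18/182 in each arm: p = 9.89%, Wilson limits 6.35% and 15.09%. Half-width = √(5.20² + 3.54²) = 6.29 points.

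| Assumed BCR, both arms | 182 per arm: events, half-width | 202 per arm: events, half-width |
|---|---|---|
| about 5% | 9, ±4.79 | 10, ±4.52 |
| about 10% | 18, ±6.29 | 20, ±5.96 |
| about 15% | 27, ±7.37 | 30, ±6.99 |

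**5. Sensitivity to classification, 182 per arm.** One man reclassified in one arm moves the difference by 1/182 = 0.55 points. Three men reclassified in the NeuroSAFE arm only (21 v 18) give 1.65 points (−4.83 to 8.15), against 0 (−6.29 to 6.29) for 18 v 18. This is a one-arm case. If three men move in both arms (21 v 21), the interval is 0 ± 6.69. How many men the conflicts affect cannot be worked out from the documents.

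**The case against.** The strongest reply is that this is an open choice. The SAP calls the outcome descriptive in three places and is to be published before unblinding. The protocol supplied no BCR method, margin or power, so the gap is partly inherited. Longer-term outcomes go to separate plans, and Protocol 6.2 intends a further oncological analysis at 5 years. The iDMC watches BCR during the trial. SAP 2.1 permits limited, justified additions, and anyone can compute a crude interval from the counts. An interval without a margin would not establish equal cure in any case.

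Most of that stands as fact. Nothing is hidden, and the interval would describe uncertainty rather than prove non-inferiority. But the 12-month comparison remains in the current protocol, and an interval that readers may derive themselves is not a commitment by the trial to report one on a fixed definition and denominator.

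Some items in the definition table are also weaker than others. The threshold matters only for a PSA of exactly 0.2. The absence of a PSA window has a stated reason, to capture oncological failure as fully as possible. An overview's silence on metastases does not contradict the body of the protocol. Men treated on trajectory are still counted by arm, under another heading. That leaves the trajectory route, the treatment label, the metastasis exclusion in SAP 3.6.5, recurrence by visit 2, and between-visit PSA values as the differences of most substance.

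**Conclusion.** The concern holds. The protocol promises a comparison of BCR between arms, and neither document plans an overall estimate of the difference with its uncertainty. The definitions in current text conflict and can classify the same man differently.

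The size is illustrative because it rests on assumed BCR rates of 5% to 15%, equal in both arms, and 182 to 202 men per arm with PSA data. On those assumptions, identical observed rates would leave an excess of about 4.5 to 7.4 points unexcluded. The primary result is not affected. One of the trial's three stated hypotheses is, and the remedy is cheap, so the change should be made before unblinding.

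**What to change.** 1. In SAP 4.9.4, pre-specify the NeuroSAFE-minus-control risk difference for BCR at 12 months with a 95% confidence interval (for example Newcombe), with no test and no margin. State the denominator: mITT men with a defined status, with men of undefined status reported by arm. Report the largest excess that the interval does not exclude.
2. Optionally, give the same for any oncological event (the first three categories of SAP 3.6.5), as supportive only. Its limits should be stated: it includes PSA persistence, which the protocol keeps out of BCR; it includes treatment decided, or only planned, by clinicians who may know the allocation; and it misses untreated men who qualify by trajectory alone.
3. Before unblinding, reconcile Protocol 2, 7.2.2.2 and 7.2.2.3 with SAP 3.3 and 3.6.5 on the trajectory route, the salvage and adjuvant labels, the time cut-off, imaging metastases, recurrence at visit 2, the threshold, and which PSA values count. Which rule is right is for the trial team to decide. If unscheduled PSA values are used, give the scheduled-visit result alongside, since extra testing could make detection differ by arm.

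The cost is SAP wording and one or two rows in a planned table. The risk difference needs no new data. Between-visit PSA values, if they are to count, may have to be entered from records. The interval will be wide and must be reported as such.

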4.10 Subgroup analysis

4.10.1 Rationale for the subgroup analysis

An important subgroup for this study is men who did not receive a pre-operative radiologist BNSR. We hypothesised that the effect of NeuroSAFE will be more beneficial in patients who did not receive a recommendation for bilateral nerve sparing. This is because our earlier analysis (Dinneen E. a.-H.-P., 2022) have demonstrated that when a patient is recommended a bilateral nerve spare based on the tumour appearing to be away from the capsule of the prostate, this is almost always correct, such that these patients to do need to have NeuroSAFE in order for the objective of maximal safe nerve sparing to be achieved. The non-BNSR subgroup therefore consists of those patients in whom NeuroSAFE offers a potential benefit.

